5.5 Dose and Dosing Schedule

NewGam is available in glass bottles with different volumes of human immunoglobulin. Glass bottles of different content should be combined in order to reach the required amount of IgG (split into infusions of 0.5 g/kg and 1.0 g/kg to maintain blinding). The total amount per patient should be dosed exactly. Partially used bottles must be discarded.

All patients should be clinically assessed for being adequately hydrated prior to infusion.

In the Dose-evaluation Phase, all patients will receive a loading dose of 2.0 g/kg Newgam (administered over two consecutive days), followed by seven infusions of the maintenance dose the patient has been randomized to (0.5, 1.0 or 2.0 g/kg NewGam), also administered over two consecutive days every 3 weeks (± 4 days). If a patient is randomized to receive the low or medium NewGam dose, the same volume with the same infusion rate as would have been applied in case the patient would have been randomized to 2.0 g/kg NewGam will be used, thus

supplemented with an authorized 0.9% w/v isotonic sodium chloride solution as appropriate and detailed in the following infusion bag split to maintain the blinding:

Treatment Arms	Infusion Bag Content	
	Day 1	Day 2*
0.5 g/kg NewGam	0.5 g/kg NewGam + 0.5 g/kg saline	1.0 g/kg saline
1.0 g/kg NewGam	0.5 g/kg NewGam + 0.5 g/kg NewGam	1.0 g/kg saline
2.0 g/kg NewGam	0.5 g/kg NewGam + 0.5 g/kg NewGam	1.0 g/kg NewGam

* Volume of Day 2 may be split up using 2 bags

The following infusion schedule must be adhered to in the Dose-evaluation Phase [all doses per kg body weight; rescue treatment only for patients who had been on 0.5 or 1.0 g/kg NewGam before, patients on 2.0 g/kg before will drop-out]:

1. Patients deteriorating* after Week 3 and before Week 6 or being stable at Week 6**

Week 0	Week 3	Week 6	Week 9	Week 12
2.0 g (LD)	0.5g 1.0 g	2.0 g (RT)	2.0 g (RT)	EOS
	2.0 g	EOS		

2. Patients deteriorating* after Week 6 and before Week 9

Week 0	Week 3	Week 6	Week 9	Week 12	Week 15
2.0 g (LD)	0.5g 1.0 g	0.5g 1.0 g	2.0 g (RT)	2.0 g (RT)	EOS
	2.0 g	2.0 g	EOS		

3. Patients deteriorating* after Week 9 and before Week 12

Week 0	Week 3	Week 6	Week 9	Week 12	Week 15	Week 18
2.0 g (LD)	0.5g 1.0 g	0.5g 1.0 g	0.5g 1.0 g	2.0 g (RT)	2.0 g (RT)	EOS
	2.0 g	2.0 g	2.0 g	EOS		

4. Patients deteriorating* after Week 12 and before Week 15

Week 0	Week 3	Week 6	Week 9	Week 12	Week 15	Week 18	Week 21

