- Documentation of concomitant medication

Visits 7, 8 and 9 (Week 15, 18 and 21)

The following assessments will be performed:

Before infusion:

- Blood sample(s) (15 mL) for safety laboratory (serum IgG, hematology and clinical chemistry)
- Grip strength
- Adjusted INCAT disability score
- I-RODS
- PI-NRS

During and after infusion:

- Administration/Infusion of IMP (0.5, 1.0 or 2.0 g/kg NewGam)
- Vital signs before, at least once during and after infusion
- Monitoring of adverse events (AEs)
- Documentation of concomitant medication

End of Study (Final) Examination

The final examination is performed three weeks after the last IMP administration (regularly at Visit 10 scheduled for Week 24 for responders), which can be either the last dose as randomized, or the last rescue dose.

The following investigations will be performed:

- Physical/neurological examination
- Blood sample (5 mL) for viral markers
- Blood samples (15 mL) for safety laboratory (serum IgG, hematology and clinical chemistry)
- Urinalysis
- Grip strength
- Adjusted INCAT disability score
- I-RODS
- MRC sum score
- Modified FSS
- PI-NRS
- NCS
- SF-36
- Monitoring of adverse events (AEs)
- Documentation of concomitant medication

After the Final Examination, the clinical study is considered completed for the patient. No further study-related assessments will be performed, unless safety concerns (e.g., ongoing AEs) require follow-up.

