6.1.4 Procedures during the Rescue Treatment

This section is only applicable for patients in the 0.5 and 1.0 g/kg NewGam arms, namely

- a) for patients deteriorating after Week 3 and before Week 18 or
- b) for patients being stable until Week 6

Depending on the time point when deterioration is detected or at Week 6 for patients remaining stable, the Rescue Treatment is initiated.

During the Rescue Treatment patients receive two doses of 2.0 g/kg NewGam in a 3-week interval; first dose at the visit when the deterioration is detected, or at the visit in Week 6 for patients remaining stable, the second dose three weeks later.

Please refer to [Section 5.5](#) for an overview on dosing if a Rescue Treatment is required.

Visit procedures at the Rescue Treatment follow essentially the same process as described for corresponding visits.

Three weeks after the second rescue dose the study termination visit is performed.

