7.2.3.4 Nerve Conduction Studies (Electrophysiological Measurements)

A pre-specified secondary endpoint in the study will be the change from baseline to the last measurement in the sum of the distal evoked amplitude of 4 right sided and 4 left sided motor nerves (peroneal, tibial, ulnar and median). All additional NCS analyses are considered exploratory (e.g. individual nerve analysis).

Electromyograph (EMG) will not be performed.

The NCS will be conducted in a standardized fashion, and a central neurology core laboratory will monitor the NCS for quality control.

The electrophysiological core lab has developed a standard electrophysiological operations manual (SOM) for each study site. All methodological details such as filter settings, rules for supramaximal stimulation, gain and sweep speed settings for tracing measurement, etc. are outlined comprehensively in the SOM.

Motor nerve studies: The median motor nerve will be tested using stimulation at the wrist and elbow; the ulnar motor nerve will be tested using stimulation at the wrist and below the elbow; the peroneal motor nerve will be tested using stimulation at the ankle and below the fibular head; and the tibial motor nerve will be tested using stimulation at the ankle. F-wave latencies will be tested in all nerves with a minimum of 10 stimulations.

Parameters measured for the motor responses will include distal and proximal onset latency, amplitude (baseline-to-peak), velocity, duration (from the onset of the waveform to the return to baseline), area (calculated by the computer), and F-wave latency.

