8.2. Withdrawals

Patients who withdraw from the study prematurely will be considered in all data presentations for which they contribute data; in particular patients who fail to perform an INCAT evaluation at week 24 will be considered to be non-responders in the analysis of the primary endpoint in the FAS.

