8.3. Handling of Missing Data

In general, missing data will not be imputed, and all data derivations will be based on observed values only; exceptions are:

In case of missing body weight, the last available weight measurement will be used for calculating the dose per kg bodyweight (last observation carried forward (LOCF)).

Because the overall disability sum score (I-RODS) cannot be calculated if not all activities are evaluated, missing items will be replaced by the latest available score of the same activity (LOCF).

If missing values occur in the confirmatory analysis of the primary endpoint in the FAS, they will be imputed by worst observed values, i.e. the patient concerned will be analyzed as non-responder.

No analyses of the patterns of missing data will be done.

For adverse events the following will be applied:

An Adverse Event (AE) is defined as treatment-emergent, if first onset or worsening is after start of the first infusion of *NewGam*.

If the start date and time of an AE are partially or completely missing, the AE will be assumed to be treatment-emergent if it cannot be definitely shown that the AE did not occur or worsen after start of the first infusion of *NewGam*. Missing dates and times will not be replaced.

For medications the following will be applied: A medication will be assumed to be concomitant if it cannot be definitely shown that the medication was not administered after start of the first infusion of *NewGam*. Missing dates will not be replaced.

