Overall patient response is defined as follows:

Yes, if clinically important improvement (i.e. MCID-SE ≥ 1.96) at week 24 and patient did not receive rescue treatment; No otherwise (including patients discontinued before week 24 and patients receiving rescue treatment).

Response based on the original MRC sum score [at Week 24]:

Yes, if increase from Week 0 by at least 4 points and patient did not receive rescue treatment; No otherwise (including patients discontinued before week 24 and patients receiving rescue treatment)

An analogue definition will be applied for response at Week 12.

Worsening based on the original MRC sum score:

Decrease to or below baseline value after temporary improvement by at least 4 points. Patients who did not temporarily improve by at least 4 points will be excluded from the analysis of time to first worsening.

Changes from baseline to termination visit in scales/scores:

When calculating those changes, values under rescue treatment will not be taken into account. Changes will be calculated to last value before start of rescue treatment.

• MRC sum score:

Though mentioned in the protocol, a modified version of the MRC sum score will not be calculated, as this modified version could not be established in other studies.

NCS measurements:

The following variables will be calculated from NCS measurements:

- Sum of all distal amplitudes: the sum will be calculated from 4 nerves, both right and left sides, for a total of 8 amplitudes. The distal sites are the ankle (lower limbs, peroneal and tibial nerves) and wrist (upper limbs, ulnar and median nerves).
- Sum of the proximal amplitudes: this will be a total sum of 6 parameters, as no proximal amplitude was measured for the tibial nerve. Proximal sites are at the fibular head (lower limb peroneal nerve) and elbow (upper limbs).
- Sum of conduction velocities (6 in total, as no conduction velocity was measured for tibial nerve)
- Sum of durations distal locations (8 in total)
- Sum of areas distal locations (8 in total)

For the last three variables, in case the result is NR (No response) in the data set, the worst value in the data set for the corresponding parameter and for the respective nerve will be used. Worst value is the highest value for durations, lowest value for area and lowest value for conduction velocity.

9. Study Subjects and Demographics

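### For FSS and SF-36 (conditionally NCS and MRC), the last-value-before-rescue rule handles early failures differently by arm: rescued lower-dose patients have only Week 0, while 2.0 g/kg failures contribute an end-of-study value

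*SAP*

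**What the plan says.** SAP 8.4 has a rule headed "Changes from baseline to termination visit in scales/scores". It sets aside values obtained under rescue and adds: "Changes will be calculated to last value before start of rescue treatment". The rule is worded alike for all arms, but Protocol 5.5 limits who can be rescued: "rescue treatment only for patients who had been on 0.5 or 1.0 g/kg NewGam before, patients on 2.0 g/kg before will drop-out".

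The protocol synopsis and flowchart schedule FSS, SF-36, MRC and NCS after randomization only at Week 12 and Termination, with the baseline at Week 0. For rescue visits, Protocol 6.1.4 says: "Visit procedures at the Rescue Treatment follow essentially the same process as described for corresponding visits". The Week 6 and Week 9 lists in Protocol 6.1.3 contain none of the four measures. At Week 12, FSS, MRC and NCS come before the infusion and SF-36 during it.

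On the end of study, Protocol 6.1.3 says: "The final examination is performed three weeks after the last IMP administration". That examination includes all four measures. SAP 8.2 keeps such data: "Patients who withdraw from the study prematurely will be considered in all data presentations for which they contribute data". SAP 8.3 imputes nothing for these measures: "all data derivations will be based on observed values only".

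The changes feed the SAP 10.2 ANCOVA models, which have dose group as a factor and the baseline value as covariate.

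**The concern.** A neutrally worded rule acts on two arms only. Patients who fail early on 0.5 or 1.0 g/kg lose every post-baseline FSS and SF-36 value: the later ones are collected, but under or after rescue, so the rule discards them. Patients who fail early on 2.0 g/kg keep theirs. If early failures do worse than other patients, the two lower arms look better relative to 2.0 g/kg for a reason unrelated to dose. Comparing the doses is a secondary objective, and Protocol 3.3.2 expects the lowest dose to be insufficient for some patients, so early failures are foreseeable.

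Two further measures may be involved.

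- **NCS sums.** The rule's heading refers to scales and scores, and NCS has its own entry in SAP 8.4. Protocol 7.2.3.4 defines the secondary NCS endpoint as "the change from baseline to the last measurement in the sum of the distal evoked amplitude". If the rule covers NCS, the same gap arises. If it does not, rescued patients contribute a post-rescue value.
- **MRC.** Protocol 3.1.3 mentions an MRC value at the time of the rescue infusion, but the visit lists for Weeks 6 and 9 have none. The gap exists only if no MRC was taken then.

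**Working it through.** **The plan's own figure.** The plan attaches no number to this rule. I take the arm sizes (35/70/35) and the 60% response rate from Protocol 9.1, whose sample size reproduces. With 62 patients, the Wilson lower limit exceeds 0.42 from 34 responders, and exact power at 60% is 83.1%. With 61 it is 79.2%, and from 62 to 80 it stays at or above 80%.

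**Step 1: cross the two schedules.** Rescue start weeks come from the five cases in Protocol 5.5 and assessment weeks from Protocol 6.1.3. Usable post-baseline values under SAP 8.4, if the rule applies to all four measures and no MRC is taken at rescue:

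| Failure identified at | 0.5 or 1.0 g/kg: FSS, MRC, NCS | 0.5 or 1.0 g/kg: SF-36 | 2.0 g/kg: all four |
|---|---|---|---|
| Week 6 | none | none | end of study, Week 6 |
| Week 9 | none | none | end of study, Week 9 |
| Week 12 | Week 12 (before infusion) | unclear (taken during first rescue infusion) | end of study, Week 12 |
| Week 15 or 18 | Week 12 | Week 12 | end of study, Week 15 or 18 |

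**Step 2: the artefact with equal failure and equal true effects.** Let f be the share failing at Week 6 or 9, m their mean change, and d the mean change in all other patients. Units are SDs of the change, and higher is better. The documents give none of these, so all three are assumptions.

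- 2.0 g/kg mean: (1-f)d + f·m
- Lower-arm mean if early failures are missing: d. Difference (2.0 g/kg minus lower arm): f(m-d).
- Lower-arm mean if Week 0 counts as the last value: (1-f)d. Difference: f·m.

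The first difference vanishes if m = d, the second if m = 0.

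**Step 3: range for f.** Rescue counts as non-response in SAP 8.4. If the planned 60% response holds in the 1.0 g/kg arm, f there cannot exceed 1 - 0.60 = 40%. At f = 10%, 20% and 40%, on average 7, 14 and 28 of 70 patients (1.0 g/kg) and 3.5, 7 and 14 of 35 (0.5 g/kg) lack a value.

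**Step 4: size under the missing reading, 2.0 minus 1.0 g/kg.** Before exclusions the SE is sqrt(1/70 + 1/35) = 0.207 SD. With exclusions and the mixture variance it is sqrt(1/(70(1-f)) + (1 + f(1-f)g²)/35), where g = d - m.

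| f | g = 0.25 SD | g = 0.5 SD | g = 1 SD |
|---|---|---|---|
| 10% | -0.025 (0.1 SE) | -0.05 (0.2 SE) | -0.10 (0.5 SE) |
| 20% | -0.05 (0.2 SE) | -0.10 (0.5 SE) | -0.20 (0.9 SE) |
| 40% | -0.10 (0.4 SE) | -0.20 (0.9 SE) | -0.40 (1.6 SE) |

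Simulating the ANCOVA with a baseline covariate (d = 0.5, m = 0) gives -0.05, -0.10 and -0.20 SD at f = 10%, 20% and 40%, matching the algebra. Under the Week 0 reading the same settings give zero, because m = 0. With m = -0.5 and f = 20%, that reading gives 0.2 × (-0.5) = -0.10 SD.

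**Step 5: unequal failure.** Assume 40%, 20% and 10% in the 0.5, 1.0 and 2.0 g/kg arms, with d = 0.5 and m = 0. Handled alike, the means are 0.30, 0.40 and 0.45, so 2.0 minus 0.5 g/kg is +0.15 SD. Under the missing reading the lower arms both become 0.50, and the difference is 0.45 - 0.50 = -0.05 SD. The shift of 0.20 SD compares with an SE of about sqrt(1/21 + 1/35) = 0.28 SD, or 0.7 SE.

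**The case against.** The strongest reply is that little hangs on this. The firm part covers FSS and SF-36, both exploratory, in exploratory models. Every input to the size is assumed, and almost every setting stays below one standard error. This stands, and it sets the severity.

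A second reply is that Week 0 is literally the last value before rescue, so these patients have zero change and are not lost. The SAP permits that reading, although SAP 8.3 more naturally makes them missing. Zero change shrinks the artefact to f·m but does not make the arms alike, since 2.0 g/kg failures still contribute an observed change.

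A third reply is that rescued patients are already visible. SAP 10.1 reports response after rescue among all rescued patients by dose group, which counts those rescued for being stable at Week 6. SAP 12.2 shows the number with non-missing values. A reader might infer that the outputs hide these patients, and the documents do not support that. What is absent is the split by rescue start week, which determines who lacks a value. The SAP 10.2 deterioration table does not cover patients stable at Week 6, and SAP 8.3 rules out missing-pattern analyses.

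A reader might also infer that the confirmatory result, or the dose comparison in general, is biased. It is not shown to be. Rescued patients are explicit non-responders in the primary and other responder definitions, and INCAT, I-RODS, grip strength and PI-NRS are measured at every visit. Nor do the documents fix a direction: the sign depends on m and d.

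**Conclusion.** The concern holds as a minor point. For FSS and SF-36, SAP 8.4 leaves lower-dose patients rescued at Week 6 or 9 with Week 0 only, and for SF-36 possibly those rescued from Week 12, while 2.0 g/kg patients failing on the same criterion contribute an observed value. That follows from the schedules and needs no assumption. The extension to the secondary NCS sum depends on whether the rule covers NCS, and the extension to MRC on whether an MRC was taken at rescue; neither should be read as established.

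The numerical size is illustrative, not an estimate. It can reach 1.6 standard errors at the ceiling of 40% early failures with a 1 SD gap. The sign reversal under unequal failure shows that the handling can matter for interpretation, but its shift is also under one standard error.

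**What to change.** Before unblinding:

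1. In SAP 8.4, state whether a patient with no post-baseline pre-rescue value is missing or has zero change in the main ANCOVA, whether the rule covers the NCS sums, and whether a Week 12 SF-36 taken during a first rescue infusion counts as pre-rescue. Reconcile this with Protocol 7.2.3.4 (NCS) and Protocol 3.1.3 (MRC).
2. For each of these endpoints, add one sensitivity ANCOVA that handles protocol-defined failure identically in all arms. Use the last scheduled Week 0 or Week 12 value taken at or before the visit at which failure is identified, with Week 0 giving zero change. A Week 12 value then counts in every arm when failure is identified at Week 12. Classify failure by the INCAT criterion in Protocol 5.5, not by the recorded drop-out reason, because consent withdrawal for ineffective therapy (Protocol 4.4.1) can occur in any arm.
3. Report by arm and rescue start week the number of patients without a post-baseline pre-rescue value.

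Observed end-of-study values regardless of rescue may be shown descriptively, labelled as including rescue effects and taken at differing weeks. They have no common time point, so they should not be presented as a treatment-policy comparison.

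The cost is SAP text, one extra exploratory model per endpoint and one count table, with no new assessments. The sensitivity model sets aside some observed 2.0 g/kg values that the main model keeps, and its zero change for early failures is itself an assumption.

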10.2. Secondary and Exploratory Efficacy Variable Analysis

All efficacy endpoints detailed in section 3.2 will be summarized by means of descriptive statistics, presented graphically as appropriate, and listed in full detail. Tables and graphs will allow for direct comparison of the different dose groups. If data are tabulated by dose group, the presentations will also include a total category, summarizing the data of all subjects in any of the dose groups. Tables for changes from baseline will include 95% confidence intervals of the mean for continuous secondary endpoints (I-RODS total score; grip strength; MRC sum score; FSS total score; NCS measurements; QoL scores) and 95% confidence intervals for the median for ordinal scales (INCAT disability sore, PI-NRS), calculated with PROC univariate option CIQUANTDF.

Similar analyses as for the primary endpoint will be performed for response variables defined based on secondary endpoints (I-RODS, grip strength, MRC sum score). These will include analysis of response rates and 95% confidence intervals, logistic regression models using the same factors as for the primary endpoint, Kaplan-Meier analyses for time to response and time to first worsening and response rates after having provided rescue medication.

Moreover, ANCOVA models will be applied for continuous secondary endpoints (I-RODS total score; grip strength; MRC sums score; FSS total score; NCS measurements; QoL scores). These ANCOVA models for changes from baseline to end of study will include dose group, randomization stratum and CIDP variant as factors and baseline value of the score/measurement as covariate. ANCOVA models will be used for calculation of least square means in various subgroups as well as for calculation of difference in least square means between the factor levels. All least square means will be presented together with 95% confidence intervals.

Any deterioration during the dose evaluation phase will be listed. Moreover, deteriorations during dose evaluation will be presented by dose group and by their effect on subject disposition (discontinuation, rescue medication).

11. Safety and Tolerability Analyses

The analysis of safety assessments in this study will be presented for the SAF.

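### The SAP scores an absent nerve response as the smallest recorded area instead of 0, and gives no rule for absent responses in the two amplitude sums

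*SAP*

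**What the plan says.** SAP 8.4 lists five variables derived from the nerve conduction studies, in this order: distal amplitude sum, proximal amplitude sum, conduction velocity sum, distal duration sum, distal area sum. For the first it says "the sum will be calculated from 4 nerves, both right and left sides, for a total of 8 amplitudes"; for the second, "this will be a total sum of 6 parameters, as no proximal amplitude was measured for the tibial nerve". A rule for absent responses (NR) follows the list: "For the last three variables, in case the result is NR (No response) in the data set, the worst value in the data set", taken for the same parameter and nerve, is used. The direction is then fixed: "Worst value is the highest value for durations, lowest value for area and lowest value for conduction velocity".

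The five sums differ in status. Protocol 7.2.3.4 states "A pre-specified secondary endpoint in the study will be the change from baseline to the last measurement in the sum of the distal evoked amplitude", taken over eight motor nerves, and classes all other nerve conduction analyses as exploratory. SAP 10.2 says "ANCOVA models will be applied for continuous secondary endpoints (I-RODS total score; grip strength; MRC sums score; FSS total score; NCS measurements; QoL scores"; the models are for change from baseline, with the baseline value as covariate.

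The general rule in SAP 8.3 is "In general, missing data will not be imputed, and all data derivations will be based on observed values only". The exceptions listed there are body weight, I-RODS items and the primary endpoint. Nerve conduction is not among them.

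**The concern.** An absent motor response is a finding, not a missing measurement. It has no duration and no velocity, so a substitute has to be chosen for those. Its amplitude and its area do have a value, which is 0. The SAP's rule does not follow that distinction in two places.

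- **Area.** The SAP substitutes the lowest recorded area for that nerve. An absent nerve then scores the same as the smallest response anyone could record, and the score depends on other patients' data.
- **Amplitude.** The rule stops at the last three variables. It therefore covers exploratory sums but not the distal amplitude sum, the one nerve conduction variable that the protocol names as a secondary endpoint.

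Absent responses mark the most severely affected nerves, and loss or return of a response is a marked change in a nerve. A rule that shrinks such a change, or that might leave it out, weakens the measure where it should be most informative.

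**Working it through.** **Inputs.** The order of the five variables, the scope of the NR rule and its direction come from SAP 8.4, the default for missing data from SAP 8.3, and the analysis model from SAP 10.2. The documents give no rate of absent responses and no typical area or amplitude, so every value below for these is assumed.

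**Counts.** Distal amplitudes: 4 nerves × 2 sides = 8. Proximal amplitudes: 3 nerves × 2 sides = 6, the tibial nerve having none. Both agree with the SAP.

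**Area, one nerve.** Let a be the area at the visit where the nerve responds and a_min the lowest recorded area for that nerve.

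- Recovered (NR, then a): with NR = 0 the change is a − 0 = a. Under the SAP it is a − a_min.
- Lost (a, then NR): with NR = 0 the change is −a. Under the SAP it is a_min − a.
- Absent at both visits: 0 either way, because a_min − a_min = 0.

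The change is understated by a_min for each nerve lost or recovered. The baseline covariate is also raised by a_min for each nerve absent at baseline. In assumed units, for a recovered nerve:

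| a | a_min | Change with NR = 0 | Change under SAP |
|---|---|---|---|
| 1.0 | 0.1 | 1.0 | 0.9 |
| 1.0 | 0.5 | 1.0 | 0.5 |
| 1.0 | 1.0 | 1.0 | 0.0 |
| 2.0 | 0.1 | 2.0 | 1.9 |
| 2.0 | 0.5 | 2.0 | 1.5 |
| 2.0 | 1.0 | 2.0 | 1.0 |

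If a zero area is already on file for that nerve, a_min = 0 and the error disappears.

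**Distal amplitude sum, one nerve.** Take seven nerves at 4 mV throughout and an eighth that is absent at baseline and returns at 0.5 mV (assumed). The correct change is +0.5 mV.

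- NR stored as 0: (28 + 0.5) − (28 + 0) = +0.5.
- NR stored as a code, sum over observed values: 28.5 − 28 = +0.5.
- NR stored as a code, all eight values required: no baseline sum, no change score, and the patient leaves the ANCOVA.

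Two of the three routes are right. The SAP does not say which applies.

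**A nerve that was not tested.** Suppose a nerve of 2 mV at baseline is simply not tested at the Termination Visit. A sum over observed values then gives −2 mV, a loss that did not happen; requiring all eight values avoids it. So if NR and not tested are both stored as non-numeric, summing observed values is right for the absent nerve and wrong for the untested one, and requiring all eight does the reverse. The two cases need separate rules.

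**Possible reach on the all-eight reading.** If each of eight nerves is absent independently with probability q, the share of patients with at least one NR at a given visit is 1 − (1 − q)^8. For q = 2%, 5%, 10% and 20% this gives 15%, 34%, 57% and 83%. Both q and independence are assumptions. Clustering of absent nerves within patients would lower these shares.

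**The case against.** The strongest reply concerns the secondary endpoint. A reader might infer from the gap that patients with absent responses drop out of the distal amplitude analysis or receive a wrong value there. The documents do not support that. A value is lost only if NR is stored as a non-numeric code and all eight amplitudes are required, and neither is stated. The phrase about a total of eight lists the components; it is not a completeness rule. Where the SAP does hold that a score cannot be formed from incomplete items, for I-RODS in SAP 8.3, it says so. The instruction there to use observed values only would give the correct sum for an absent nerve. Amplitude may also have been left out on purpose because its NR value is already 0, and the core laboratory's operations manual, which is not available here, may settle the coding. All of this stands.

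It does not remove the gap. If the authors took NR as 0 for amplitude, the same reasoning gives 0 for area, and the SAP does not use it. SAP 8.4 also lets further derivations for secondary variables be described in the study report without an amendment, so the choice could be made late.

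On area, one can say that the rule is pre-specified, never ranks an absent nerve above a recorded one, affects only an exploratory variable, and may do little if the lowest recorded area is near 0. That limits the size of the error, but it does not make the substituted value right.

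**Conclusion.** The area rule is wrong as written. Unless a zero is recorded, it gives an absent nerve a positive area and understates the change, by the lowest recorded area for that nerve, whenever a response is lost or recovered. The error cannot be sized from the documents and is confined to an exploratory variable.

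For the two amplitude sums, including the distal sum that is a secondary endpoint, the finding is a missing rule and not a demonstrated error. Patients with an absent nerve may drop out of the ANCOVA under one combination of storage and completeness; under the other routes shown, the sum is correct. The shares of 15% to 83% describe only that one combination, under assumed rates and independence, and should not be read as expected losses.

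The primary endpoint and the sample size are not affected.

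**What to change.** Before unblinding, state in SAP 8.4 that:

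- no response counts as 0 for distal amplitude, proximal amplitude and distal area;
- the worst-value rule applies only to durations and conduction velocities, which have no natural value when there is no response;
- a nerve that was not tested, or whose recording was technically invalid, is missing and not 0, and the sum is not formed at that visit.

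The cost is a few sentences and a small recode, with no new data. If NR amplitudes are already stored as 0, scoring NR as 0 leaves the amplitude results unchanged. The third rule gives up a sum when a nerve is untested. The alternative of using only nerves valid at both visits would keep those patients, but the number of nerves would then differ between patients and the ANCOVA would have no defined eight-nerve baseline for them.
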